7.5.3 Opioid Free (OF) Outcomes

Opioid use is recorded on the rescue medication eCRF from the end of surgery through the D15 follow up/Early termination (ET). If additional opioids, other than the study rescue medications, appear on the concomitant medications page and can be identified, those opioids will also be considered.

The percentage of subjects who do not require opioids (are Opioid Free or OF) will be analyzed using a logistic regression with treatment group (4 levels) as the main effect. The analysis will compare the odds ratios of the proportions of OF subjects between each treatment group and the placebo group. A summary of frequencies as well as odds ratio, 95% confidence intervals and p-values will be presented for 0 to 96 hours (OF_{0 to 96h}), 24-96 hours (OF_{24 to 96h}), 96 hours to Week 1 (OF_{96h to w1}) and 96 hours to Week 2 (OF_{96h to w2}).

7.5.4 Total Opioid Consumption (in Daily Oral Morphine Equivalents)

The amount of opioids taken as rescue will be calculated using the rescue medication page of the eCRF. If additional opioids, other than the study rescue medications, appear on the concomitant medications page and can be identified, those opioids will also be included (in terms of morphine equivalents) in the total consumed. [Table 7-1](#) will be used to calculate the morphine equivalent dose (MED) for each medication. The total opioid consumption for each day for each subject will be calculated as the sum of the MEDs of all of the medications taken on that day. For example, if a subject takes 5 MED morphine on Day 1 and Day 2, and 10 MED of Oxycodone on Day 2, the total consumption for Day 1 is 5 MED, and the total consumption for Day 2 is 15 MED. Subjects that take no opioids on a day will have a total opioid consumption value of zero for that day.

Table 7-1 Table of Equianalgesic Conversion

Opioid (Doses in mg)	Conversion Factor
Hydrocodone	1
Hydromorphone	4
Morphine	1
Oxycodone	1.5
Tramadol	0.1
Multiply the opioid dose by the conversion factor = morphine equivalent dose (MED): e.g., oxycodone 5 mgX1.5 = 7.5 mg MED	

Total opioid consumption will be calculated overall and for the same periods as the NRS AUC values: 0-96 hours ($OC_{0 \text{ to } 96h}$), 24-48 hours ($OC_{24 \text{ to } 48h}$), 24-72 hours ($OC_{24 \text{ to } 72h}$) and 24-96 hours ($OC_{24 \text{ to } 96h}$). In addition, analgesic consumption (AC) from T96h to W1 ($AC_{96h \text{ to } W1}$) and AC_{96h} to W2 will also be summarized. An ANOVA with treatment arm as the main effect will be performed and the same types of comparisons as described in Section 7.4.1 will be presented. A separate summary containing only subjects that have taken at least one dose of rescue will be performed if warranted.

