### 15.6.4. Handling of Dropouts and Missing Data

All efforts will be made to minimize missing data. These efforts will include the following:

- Subjects are required to consent continuous data collection even after subjects discontinue the study treatment;
- Continue data collection after subjects taking rescue medication;
- Establish robust efficacy data collection procedures.

With the procedures above, it is expected that the missing would be minimal.

For subjects who take rescue medication a windowed last pain score carried forward (LOCF) will be used. The pre-rescue pain score will be used to impute scheduled assessments for 4 hours following the rescue use. Intermittent missing pain scores (due to subject sleeping, etc.) will not be imputed, and AUC will be calculated based on non-missing values. For subjects who drop out of the study prior to Day 15, scheduled assessments will first be imputed using the worst prior pain score carried forward (WOCF). As sensitivity analyses, the AUC will also be calculated where assessments after drop out will be imputed using LOCF, using the last scheduled non missing pain score prior to drop out.

For secondary continuous efficacy endpoints, similar methods as the primary analysis will be used. For categorical endpoints, when assessments are imputed for data after a subject discontinues from the study, a WOCF method will be used.

Sensitivity analysis of the primary efficacy variable using different methods of imputation for rescue medication may also be performed. Additional sensitivity analysis with different missing value imputation methods for subjects who drop out of the study may also be performed. All imputation methods for pain intensity will be documented in the SAP.

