4 SUBJECT POPULATIONS

4.1 Analysis Populations

Six analysis populations are defined as follows:

- **Intent-to-treat (ITT)** population: all subjects who are randomized. Subjects will be analyzed according to the treatment they were randomized to.
- **Modified intent-to-treat (mITT)** population: all subjects who receive a full dose of study treatment and complete the first 3 pain assessments (through T2h). Subjects will be analyzed according to the treatment they were randomized to.
- **In patient study completer (Inpatient CP)**: all subjects who receive a full dose of study treatment and complete the inpatient assessment period (through T96h). Subjects will be analyzed according to the treatment they were randomized to.
- **Study Completers (CP)**: all subjects who receive a full dose of study treatment and complete the entire study period through D29±2/W4. Subjects will be analyzed according to the treatment they were randomized to.
- **Safety** Population will include all randomized subjects who received any amount of study drug. subjects will be analyzed by treatment group according to the actual treatment received, i.e., “as treated”.
- **Pharmacokinetic (PK)** population: All randomized participants who received a full dose of study drug and complete all PK assessments through the first 6 hours (T6h) time point. Note, subjects who fail to complete these PK assessments will be replaced.

Analysis populations will be determined before study unblinding.

The primary and secondary efficacy analyses will be performed using mITT population. Efficacy analyses will also be carried out using ITT, Inpatient CP and/or CP populations for selected endpoints as appropriate. Baseline characteristics will be summarized using ITT population and safety endpoints will be summarized using Safety population. PK summaries will be presented using the PK population.

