For subjects who take prohibited medication, NRS results collected after taking the prohibited medication will not be used for AUC calculations but will be imputed according to the methods used for discontinued subjects.

Intermittent missing pain scores at rest or after ambulation (due to subject sleeping, etc.) will not be imputed, and AUC will be calculated based on non-missing values. For subjects who drop out of the study or take prohibited medication prior to Day 15, scheduled assessments will first be imputed using the worst prior pain score carried forward (WOCF).

Two sensitivity analyses will be performed to evaluate the robust of the primary result:

- 1) AUC will be calculated where assessments after drop out will be imputed using LOCF, using the last scheduled non missing pain score prior to drop out.
- 2) AUC will be calculated where assessments after dropping out will be imputed using the median score from the remainder of subjects in the group continuing in the study.

For secondary continuous efficacy endpoints, similar methods as the primary analysis will be used. For categorical endpoints, when assessments are imputed for data after a subject discontinues from the study, a WOCF method will be used.

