7.5.5 Time to First Use of Rescue Medication

For the analysis of time to use of rescue medication, only OPIOID rescue medication will be included,

The time to first rescue will be measured from Time 0 (time of completion of study drug administration) and 24 hours post-dose. If a subject does not take rescue medication but prematurely discontinues from the study, then for analysis purposes the subject's observation time will be the time of the discontinuation. The observation time will be considered to be a rescue event if the discontinuation was due to LOE, otherwise, it will be considered a censored observation.

The distributions of time to first rescue in each treatment group will be presented graphically using Kaplan-Meier plots.

If data warrant, a summary table will present the number of subjects receiving rescue medication, number of censored subjects, median time to first dose of rescue, and 95% confidence intervals of the medians by treatment groups. Individual times to event will be listed. Subjects will be followed at the time of discontinuation if no rescue medication was received prior to discontinuation. For the time to first rescue medication after 24 hours post-dose, subjects will be censored at 24 hours if the subject drop out the study prior to Hour 24.

Time to second rescue will also be explored for subjects who receive the first rescue prior to 60 minutes post-dose. Subjects will be censored at the time of discontinuation if the subject receives only 1 rescue medication. The observation time will be considered to be a rescue event if the discontinuation was due to LOE, otherwise, it will be considered a censored observation

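### The SAP does not carry its dropout rule into OF0-96h and OC0-96h, so a subject who leaves before T96h without opioid use can count as opioid-free with zero consumption

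*SAP*

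**What the plan says.** - **Place in the testing order.** SAP 7.3 tests OF0-96h first and OC0-96h second, 4.2 mg against placebo, each two-sided at 0.05, once the primary endpoint has succeeded. After a non-significant result the remaining key secondary tests are exploratory.
- **Population.** The analyses use mITT (SAP 4.1), which needs a full dose and the first three pain scores, up to T2h.
- **OF.** SAP 7.5.3: "The percentage of subjects who do not require opioids (are Opioid Free or OF) will be analyzed using a logistic regression" with treatment as a four-level effect. Opioid use is captured from the end of surgery to D15 or early termination, and identifiable opioids on the concomitant medication page also count. Nothing sets the status of a subject whose 0-96 h window is incomplete.
- **OC.** SAP 7.5.4 adds up the morphine equivalents (MED) taken each day and states: "Subjects that take no opioids on a day will have a total opioid consumption value of zero for that day". Discontinuation is not mentioned.
- **General dropout rule.** SAP 7.1: "For secondary continuous efficacy endpoints, similar methods as the primary analysis will be used", and "For categorical endpoints, when assessments are imputed for data after a subject discontinues from the study, a WOCF method will be used". Protocol 15.6.4 has the same rule. For the primary endpoint, the method is to carry the worst earlier pain score forward.
- **Related endpoints.** For time to first rescue, when a subject discontinues without rescue, SAP 7.5.5 says: "The observation time will be considered to be a rescue event if the discontinuation was due to LOE"; other such discontinuations are censored. SAP 7.5.7 assumes that dropout for an adverse event (AE) or lack of efficacy (LOE) is pain related.
- **Outputs.** In SAP 14.1.1 the AUC analysis tables are labelled WOCF, LOCF or Median. The OF and OC tables carry no imputation label.

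**The concern.** WOCF works for pain scores because a subject who leaves has usually reported some pain, and the worst of it is carried on. OF and OC are built differently: they record whether, and how much, opioid was taken over a window. If the window is cut short before any opioid is taken, the worst status so far is still opioid-free and the worst consumption so far is still zero. The rule meant to be conservative then returns the most favourable value.

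For a leaver who has taken opioid, the general rule is not turned into a consumption rule. The SAP does not say whether the worst dose, calendar day or 24-hour window is carried forward. A programmer working from 7.5.4, with data capture ending at early termination, could read the zero sentence as covering the days after departure.

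At stake are the first two gated tests. A wrong call on OF0-96h either lets the sequence continue when it should stop, or stops it when it should continue.

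**Working it through.** **1. The plan's own figure.** The documents state no dropout, OF or OC rate. The only planning figure is 36 per arm for 90% power on AUC0-96h (SAP 2.2.4), from a difference of 100 and an SD of 130:

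n = 2 × (1.960 + 1.282)² × 130² / 100² = 35.5, rounded up to 36.

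Power at n = 36 is 0.904 by the normal formula and 0.896 to 0.900 by the t distribution, so the figure reproduces. It matters here only because it gives the arm size.

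**2. What the stated rules return for an mITT subject.**

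| Subject | OF0-96h | OC0-96h | Time to first rescue (7.5.5) |
|---|---|---|---|
| Leaves before T96h for LOE, no opioid taken | Opioid-free under literal WOCF | 0 | Rescue event |
| Leaves before T96h for another reason, no opioid taken | Opioid-free under literal WOCF | 0 | Censored |
| Leaves before T96h after taking opioid | Not opioid-free, whatever follows | Recorded doses only if later days are set to zero; more if a worst day is carried forward | Event at first dose |

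The first two rows are the defect in OF. The third affects OC only.

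**3. Size for OF (assumed counts, 36 per arm).** One subject is 1/36 = 2.8 percentage points. With treatment as the only factor, the logistic comparison of two arms is the Wald test of the log odds ratio: z = ln(OR) / √(1/a + 1/b + 1/c + 1/d), where a to d are the four cell counts.

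- 10/36 active against 2/36 placebo: OR = (10 × 34)/(26 × 2) = 6.54, ln = 1.878, SE = 0.817, z = 2.298, p = 0.022.
- One active leaver rescored as not opioid-free (9/36 against 2/36): OR 5.67, p = 0.035.
- Two rescored (8/36 against 2/36): OR 4.86, p = 0.057.
- From 12/36 against 4/36 (p = 0.030), rescoring one active leaver gives 11/36 and p = 0.050; rescoring two gives 10/36 and p = 0.083.
- Opposite direction: start at 10/36 against 4/36 (p = 0.083). If two of the four placebo successes were leavers, rescoring them gives 10/36 against 2/36 and p = 0.022.

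**4. Size for OC (assumed use).** One 5 mg oxycodone dose is 5 × 1.5 = 7.5 mg MED (SAP Table 7-1).

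- Upper bound: for a departure at T24h, the inpatient schedule after 12 h (every 4 h, Protocol 9.1.3) allows (96 − 24)/4 = 18 further doses, or 18 × 7.5 = 135 mg MED unobserved.
- Example: three doses a day is 3 × 7.5 = 22.5 mg MED. A subject leaving at T24h scores 22.5 if later days are set to zero, against 4 × 22.5 = 90 if that day is carried forward.
- Effect on the arm mean: (leavers/36) × daily use × 3 days. One leaver at 15 mg/day gives 1/36 × 15 × 3 = 1.25 mg; four at 45 mg/day give 4/36 × 45 × 3 = 15 mg.

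**The case against.** The case on the other side has real force.

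- **No sentence scores dropouts as zero or opioid-free.** A reader might infer that SAP 7.5.4 lays this down. It does not: the zero sentence concerns days on which no opioid is taken and can be read as covering observed days only, with 7.1 covering dropout. This stands. For a leaver with earlier opioid use, zero-filling is a possible reading, and carrying the worst day forward is at least as natural. SAP 3 lets specific sections override general policies, but that concerns the conventions in section 3 itself and does not settle 7.1 against 7.5.4.
- **Not every dropout gains.** A reader might infer that all early leavers get the best result on both endpoints. Any opioid before departure already makes the subject not opioid-free, and those doses still count in OC. Only a leaver with no opioid use can get the best value on both.
- **Time to first rescue is a different endpoint.** It lies outside the hierarchy and censors non-LOE leavers, so calling the plan self-contradictory goes too far. The sections do differ in spirit: an LOE leaver is presumed to need rescue in 7.5.5 and can be a success in 7.5.3.
- **Exposure is limited.** Subjects are inpatients to T96h, discontinuers are asked to continue assessments to T96h unless they withdraw from everything (SAP 2.2, Protocol 15.3), rescue is available on request within protocol timing, and SAP 7.1 expects little missing data. This makes cases rare but supplies no rule for those that occur.

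None of this answers the central case. For a leaver without opioid use, applying 7.1 exactly as written produces the favourable score.

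**Conclusion.** The point holds as a gap that should be closed before database lock. The general WOCF rule is not worked out for OF0-96h and OC0-96h. Taken literally, it credits unobserved time as success for a subject who leaves before T96h without opioid. For other leavers, OC is open to two readings, one of which understates use.

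The size cannot be fixed from the documents. At 36 per arm, one or two such leavers can move OF across 0.05, but only when the result is already close; the counts in the working are assumptions chosen to show this. The OC effect on an arm mean is 1.25 to 15 mg MED over the assumed range of one to four leavers at T24h using 15 to 45 mg/day.

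A reader might also infer a bias in favour of CA-008. The documents do not support that. The direction depends on which arm loses more such subjects, and more placebo leavers would work against CA-008.

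**What to change.** **SAP 7.5.3.** State that a subject not observed through T96h is not counted as opioid-free for OF0-96h. The minimum is to apply this to LOE and AE discontinuations, in line with 7.5.5 and 7.5.7. Add a sensitivity analysis using observed status.

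**SAP 7.5.4.** State that the zero rule applies only to days under observation, and that OC after discontinuation follows a defined analogue of the primary WOCF, for example the subject's worst observed 24-hour consumption. Define this for a subject with less than 24 hours of data. A leaver with no opioid use would still score zero under this rule, so that case needs its own line. One option is a sensitivity analysis using the median consumption of subjects in the group who continue, mirroring the second sensitivity analysis in 7.1.

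**SAP 14.1.1.** Label the OF and OC tables with the method used.

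**Cost.** A few sentences and a little extra analysis, with slightly lower OF rates. Carrying a worst 24 hours forward can overshoot for an early leaver: the inpatient schedule allows six doses in the first 12 h and three in the next 12 h, or 9 × 7.5 = 67.5 mg MED, against 6 × 7.5 = 45 mg in any later 24 h. The OC sensitivity analysis would show whether this matters.

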7.5.5 Time to First Use of Rescue Medication

For the analysis of time to use of rescue medication, only OPIOID rescue medication will be included,

The time to first rescue will be measured from Time 0 (time of completion of study drug administration) and 24 hours post-dose. If a subject does not take rescue medication but prematurely discontinues from the study, then for analysis purposes the subject's observation time will be the time of the discontinuation. The observation time will be considered to be a rescue event if the discontinuation was due to LOE, otherwise, it will be considered a censored observation.

The distributions of time to first rescue in each treatment group will be presented graphically using Kaplan-Meier plots.

If data warrant, a summary table will present the number of subjects receiving rescue medication, number of censored subjects, median time to first dose of rescue, and 95% confidence intervals of the medians by treatment groups. Individual times to event will be listed. Subjects will be followed at the time of discontinuation if no rescue medication was received prior to discontinuation. For the time to first rescue medication after 24 hours post-dose, subjects will be censored at 24 hours if the subject drop out the study prior to Hour 24.

Time to second rescue will also be explored for subjects who receive the first rescue prior to 60 minutes post-dose. Subjects will be censored at the time of discontinuation if the subject receives only 1 rescue medication. The observation time will be considered to be a rescue event if the discontinuation was due to LOE, otherwise, it will be considered a censored observation

7.5.6 PGE and IGE

The proportions of subjects in each individual PGE or IGE category will be summarized by treatment group and analyzed using the Cochran-Mantel-Haenszel (CMH) mean score test (using equally spaced scores) at each time point (Weeks 1, 2 or 4) to compare treatments across the 4 levels of outcomes (poor, fair, good, or excellent). In addition, Fisher's exact test will be performed to compare treatments across 2 levels of outcomes (Poor/Fair versus Good/excellent).

Individual PGE and IGE scores will be listed.

7.5.7 Number and Percentage of Subjects Who Drop Out due to AE or Lack of Efficacy (LOE) During the Inpatient Period

Proportion of subjects who drop out of the study due to AE or LOE during the inpatient periods (24 to 96 (LOE_{24 to 96h}) and 0 to 96 hours (LOE_{0 to 96h})) will be analyzed using Fisher's exact tests. If a subject drops out of the study due to AE or LOE, it is assumed that drop out is pain related. The reasons for discontinuation as documented on the eCRF end of study page will be used to determine the subjects who drop out for AE or LOE. Subjects who drop out of the study prior to 24 hours will be excluded from LOE_{24 to 96h} analysis.

A summary table will present the active vs. placebo group proportions, 95% confidence intervals and two-sided Fisher's exact p-values for the difference in proportions between each active group and placebo.

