
Other Endpoints:
	
 
● <math>AUC_{0\text{ to }24h}</math>, <math>AUC_{0\text{ to }120h}</math>, <math>AUC_{0\text{ to }W1}</math> (walking), <math>AUC_{0\text{ to }W2}</math>, <math>AUC_{0\text{ to }W2}</math> (walking), <math>AUC_{12\text{ to }24h}</math>, <math>AUC_{24\text{ to }48h}</math>, <math>AUC_{24\text{ to }72h}</math>, <math>AUC_{24\text{ to }96h}</math>, <math>AUC_{96h\text{ to }120h}</math>, <math>AUC_{96h\text{ to }W1}</math>, <math>AUC_{24h\text{ to }W1}</math>(walking), <math>AUC_{96h\text{ to }W2}</math>, <math>AUC_{96h\text{ to }W2}</math>(walking)
 
● <math>OC_{24\text{ to }48h}</math>, <math>OC_{24\text{ to }72h}</math>, <math>OC_{24\text{ to }96h}</math>
 

	
 
• OF24 to 96h, OF96h to W1 and OF96h to W2
 
• TTFRafter T0 and TTFRafter T24h
 
• Analgesic consumption from T96h to W1 (AC96h to W1) and AC96h to W2
 
• PGE comparing the %age of subjects reporting “poor” + “fair” vs. “good” + “excellent” responses, and the %age reporting each category of response at W1, W2 and W4
 
• IGE comparing the %age of those reporting “poor” + “fair” vs. “good” + “excellent” responses, and the %age reporting each category at W1, W2 and W4
 
• Number and %age subjects with an AE of lack of efficacy (LOE) during the inpatient period: LOE0 to 96h
 
• HCU96h to W2 and HCU96h to W4
 

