### **10.3. Removal of Subjects from Therapy or Assessment**

A subject is free to withdraw consent and discontinue participation in the study at any time for any reason. A subject's participation must therefore be terminated immediately upon his/her request, and the reason(s) for discontinuation appropriately documented.

A subject may be discontinued from the study for any of the following reasons:

- Safety reasons, including AEs or significant concomitant illness, injury, or urgent surgeries/procedures that would, in the judgment of the investigator, affect assessments of clinical status to a significant extent, require discontinuation of study treatment, or both
- At the request of the Sponsor, regulatory agency, or Institutional Review Board (IRB)
- Subject is lost to follow-up
- Subject treatment allocation is unblinded (i.e., individual code break; [Section 11.5](#))
- Death of subject
- A subject may also be discontinued from the study, at the discretion of the investigator and/or Sponsor, for any of the following reasons:
  - Subject refuses or is unable to adhere to the study protocol
  - Major protocol violation
  - Pregnancy
  - Use of unacceptable concomitant medication(s)
  - It is not considered in the best interest of the subject to continue
  - Administrative reasons (e.g., termination of enrollment or study)

The Investigator must maintain a record of all subjects who discontinue from the study prior to completion; the reason(s) for study discontinuation will be documented. If a subject chooses to

withdraw from the study, the Investigator should make a reasonable attempt to obtain and record the reason(s) for withdrawal in as much detail as possible, although the subject is not obligated to provide such a reason.

If a subject is discontinued while at the clinical site, the early termination procedures should be performed prior to discharge from the clinical site. The investigator should ask the subject to participate in follow-up procedures, provided that the subject has not withdrawn consent for such procedures. If the subject refuses to complete early termination/follow-up procedures or continued data collection, this information will be recorded.

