#### 12.6.1.3. Other Efficacy Endpoints

- $AUC_{0\text{ to }24h}$ ,  $AUC_{0\text{ to }120h}$ ,  $AUC_{0\text{ to }W1}$  (walking),  $AUC_{12\text{ to }24h}$ ,  $AUC_{24\text{ to }48h}$ ,  $AUC_{24\text{ to }72h}$ ,  $AUC_{24\text{ to }96h}$ ,  $AUC_{96h\text{ to }120h}$ ,  $AUC_{96h\text{ to }W1}$ ,  $AUC_{24h\text{ to }W1}$ (walking),  $AUC_{96h\text{ to }W2}$ ,  $AUC_{96h\text{ to }W2}$ (walking)
- $OC_{24\text{ to }48h}$ ,  $OC_{24\text{ to }72h}$ ,  $OC_{24\text{ to }96h}$

- OF24 to 96h, OF96h to W1 and OF96h to W2
- TTFRafter T0 and TTFRafter T24h
- Analgesic consumption of OTC analgesics and if prescribed, oxycodone, from T96h to W1 and T96h to W2
- PGE comparing the %age of subjects reporting “poor” + “fair” vs. “good” + “excellent” responses, and the %age reporting each category of response at W1, W2 and W4
- IGE comparing the %age of those reporting “poor” + “fair” vs. “good” + “excellent” responses, and the %age reporting each category at W1, W2 and W4
- Number and %age Subjects with an AE of lack of efficacy (LOE) during the inpatient period: LOE24 to 96h, LOE0 to 96h
- HCU96h to W2 and HCU96h to W4

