7.4.3 Other Efficacy Endpoints

- AUC of subject's NRS will be examined over various time periods: $AUC_{0 \text{ to } 6h}$, $AUC_{0 \text{ to } 12h}$, $AUC_{0 \text{ to } 24h}$, $AUC_{0 \text{ to } 120h}$, $AUC_{0 \text{ to } w1}$ (walking), $AUC_{0 \text{ to } w2}$, $AUC_{0 \text{ to } w2}$ (walking), $AUC_{12 \text{ to } 24h}$, $AUC_{24 \text{ to } 48h}$, $AUC_{24 \text{ to } 72h}$, $AUC_{24 \text{ to } 96h}$, $AUC_{96 \text{ to } 120h}$, $AUC_{96h \text{ to } w1}$, $AUC_{24h \text{ to } w1}$ (walking), $AUC_{96h \text{ to } w2}$, $AUC_{96h \text{ to } w2}$ (walking).
- Time-specific ("milestone") mean pain intensity NRS at 6, 12, 24, 28, 72, 96, 120, 144, and 168 hours
- Time-specific ("milestone") mean pain intensity NRS by site at 6, 12, 24, 28, 72, 96, 120, 144, and 168 hours
- OC over following time periods: $OC_{24 \text{ to } 48h}$, $OC_{24 \text{ to } 72h}$, $OC_{24 \text{ to } 96h}$.
- OF over following time periods: $OF_{24 \text{ to } 96h}$, $OF_{96h \text{ to } w1}$, $OF_{96h \text{ to } w2}$.
- Time to first use of rescue medication ($TTFR_{\text{after } T0}$) and first use after 24 hours ($TTFR_{\text{after } T24h}$). For the analysis of time to use of rescue medication, only OPIOID rescue medication will be considered,
- Analgesic consumption (AC) from T96h to W1 ($AC_{96h \text{ to } W1}$) and $AC_{96h \text{ to } W2}$.
- Patient global evaluation (PGE) comparing the percentage of subjects reporting (poor or fair) versus (good or excellent) responses and the percentage reporting each category of response at W1, W2 and W4.
- Investigator's global evaluation (IGE) comparing the percentage of those reporting (poor or fair) versus (good or excellent) responses and the percentage reporting each category at W1, W2 and W4.
- Number and percentage of subjects who drop out due to an AE or lack of efficacy (LOE) during the inpatient period: $LOE_{24 \text{ to } 96h}$, $LOE_{0 \text{ to } 96h}$.

- Health care utilization after discharge from the inpatient unit: HCU_{96h to W2} and HCU_{96h to W4}. (Not included in this SAP)

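### SAP 7.4.3 and 7.5.7 replace the protocol's lack-of-efficacy endpoint with an AE-or-LOE dropout composite, keep the LOE labels, and assume every such dropout was about pain

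*SAP*

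**What the plan says.** Protocol 12.6.1.3 lists this among the other efficacy endpoints, for both 24-96h and 0-96h: "Number and %age Subjects with an AE of lack of efficacy (LOE) during the inpatient period". The synopsis gives the same definition for 0-96h. Neither requires the subject to leave the study, and neither counts other AEs.

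SAP 7.4.3 uses the same two LOE labels for a different event: "Number and percentage of subjects who drop out due to an AE or lack of efficacy (LOE) during the inpatient period". SAP 7.5.7 takes the cause from the recorded discontinuation reason, "as documented on the eCRF end of study page will be used to determine the subjects who drop out for AE or LOE", and then states: "If a subject drops out of the study due to AE or LOE, it is assumed that drop out is pain related". Each active group is compared with placebo by a two-sided Fisher's exact test. The output is Table 14.2.8, on the mITT population.

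Protocol 10.3 lets a subject be discontinued for reasons that need not involve pain: "Safety reasons, including AEs or significant concomitant illness, injury, or urgent surgeries/procedures".

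SAP 7.5.5 (time to first rescue) covers subjects who discontinue without having taken rescue. There the observation time is "considered to be a rescue event if the discontinuation was due to LOE, otherwise, it will be considered a censored observation".

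SAP section 12, which is meant for changes from the protocol's analyses, names none and defers to the study report.

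**The concern.** The SAP event is both wider and narrower than the protocol's. It is wider because it takes in any dropout attributed to an AE, whether or not pain was involved. It is narrower because a subject with an LOE event who takes rescue and stays is no longer counted. Staying is what the protocol encourages: rescue is available throughout the inpatient period (Protocol 9.1.3), and subjects who discontinue are asked to continue assessments through T96h (Protocol 15.3).

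The assumption about pain is what lets the composite carry an efficacy label, and nothing in the plan checks it. No step reviews whether the AE behind a dropout was pain.

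At stake is the meaning of one efficacy result. Tolerability and analgesic failure would be mixed under a label that the protocol reserves for analgesic failure, and a reader who compares the result with the protocol would not be told that the definition had changed.

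**Working it through.** **Step 1. The plan's own figure.** The only sizing figure concerns the primary AUC (SAP 2.2.4): difference 100, SD 130, two-sided 0.05, 90% power.

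n per arm = 2 × (1.960 + 1.282)² × (130/100)² = 2 × 10.51 × 1.69 = 35.5, rounded up to 36.

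Power at 36 per arm is 0.904 by the normal approximation (noncentral t: 0.896 with 70 df, 0.900 with 140 df). The figure reproduces, and this point does not change it. No rate, power or sample size is given for the LOE endpoint.

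**Step 2. The rules side by side**, for a subject in the inpatient period:

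| Subject | Protocol 12.6.1.3 | SAP 7.5.7 | SAP 7.5.5, no prior rescue |
|---|---|---|---|
| LOE recorded as an AE, stays | event | not an event | depends on later rescue |
| Leaves for LOE, LOE recorded as an AE | event | event | event |
| Leaves for LOE, no LOE AE recorded | not an event, read literally | event | event |
| Leaves for an AE unrelated to pain | not an event | event | censored |

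The first and last rows show the narrowing and the widening.

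**Step 3. Weight of one subject.** 1/36 = 0.028, or 2.8 percentage points of a planned arm. The real denominator may differ slightly, because the table uses mITT and the 24-96h version leaves out dropouts before 24 hours.

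**Step 4. Illustration with assumed counts** (not in the documents), 36 per arm, two-sided Fisher's exact test, active v placebo.

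For 0 v 6: p = 2 × C(36,6)/C(72,6) = 2 × 1,947,792/156,238,908 = 0.025.

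- Non-pain AE dropouts added to active: 1 v 6, p = 0.107; 2 v 6, p = 0.260; 3 v 6, p = 0.478. A benefit is hidden.
- One non-pain AE dropout added to placebo: 0 v 5 (p = 0.054) becomes 0 v 6 (p = 0.025). A benefit is exaggerated.
- One of six placebo LOE events occurs in a subject who stays: 0 v 6 (p = 0.025) becomes 0 v 5 (p = 0.054). An event is missed.

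**Step 5. Power over a range of assumed rates.** Active LOE is set to 0%. The composite rate in an arm is 1 − (1 − LOE)(1 − AE). For placebo LOE of 20% and AE dropout of 3%, it is 1 − 0.80 × 0.97 = 0.224.

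| Non-pain AE dropout, active / placebo | Placebo LOE 20% | Placebo LOE 10% |
|---|---|---|
| none | 75.4% | 14.5% |
| 3% / 3% | 59.4% | 13.8% |
| 5% / 2% | 41.8% | 6.2% |
| 10% / 2% | 17.8% | 1.9% |

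If LOE is as uncommon as 10% on placebo, even the clean endpoint has little power, so the loss then matters more for interpretation than for the test.

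**The case against.** The best defence is that the composite is openly named. The 7.5.7 heading says AE or LOE, and Table 14.2.8 is titled as an analysis of dropout. A reader might infer that the SAP has made LOE mean dropout for any AE, or that a CA-008 safety dropout would be tabulated outright as lack of efficacy. The documents do not support that: LOE dropout remains part of the event, and the efficacy reading comes only from the LOE labels and the one sentence about pain. Those are still enough to mislead.

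The composite may also catch real failures. Protocol 10.3 does not name lack of efficacy among the discontinuation reasons, and the protocol treats LOE as an AE, so a withdrawal for pain could be recorded as an AE. The protocol has no rule for recording an inpatient LOE event; its instruction to capture persistent pain as an AE covers the outpatient period. This stands as a reason to define the terms. It does not justify assuming that all AE dropouts are about pain.

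A reader might also see 7.5.5 and 7.5.7 as a contradiction. They concern different endpoints, and 7.5.5 censors an AE dropout only if no rescue was taken before. The fair statement is that the pain assumption fits poorly with 7.5.5, which already treats LOE as a separable reason.

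Finally, the causes can be partly separated from other planned output: withdrawal reasons by group (SAP 4.2, Table 14.1.1), AEs leading to discontinuation (Table 14.3.1.5, Listing 16.2.18.4) and AEs by preferred term (Table 14.3.1.2). That stands, but the planned Fisher test still uses the pooled event.

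**Conclusion.** The point holds on the text and is minor. The SAP substitutes an AE-or-LOE dropout composite for the protocol's endpoint, keeps its labels, adds an unsupported assumption about cause, and does not list the change in section 12. Non-pain AE dropouts count as efficacy failures, and LOE events in subjects who stay are missed.

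The damage is confined to an other endpoint tested at 0.05 without multiplicity adjustment (SAP 7.3). The primary AUC imputes dropouts by its own rule regardless of reason (SAP 7.1), and neither it nor the key secondary hierarchy depends on this definition.

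Two further inferences are not supported. One is that the bias favours or harms CA-008 in particular: the direction depends on which arm has the non-pain dropouts and which has the LOE events in subjects who stay. The other is that a single misclassified subject would decide the result: the documents give no LOE or AE dropout rate, and the p-values and power figures above rest on assumed counts and rates.

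**What to change.** - Analyse LOE 0-96h and LOE 24-96h as Protocol 12.6.1.3 defines them: subjects with an AE of lack of efficacy. Name the qualifying MedDRA preferred terms in the SAP before unblinding.
- If LOE as the recorded discontinuation reason is also to count, say that this extends the protocol definition and list it in SAP section 12.
- Report AE dropout and LOE dropout on separate lines of Table 14.2.8. If a composite is kept, label it as all AE/LOE dropout, not LOE.
- Delete the sentence in 7.5.7 that assumes dropout is pain related. This also removes the awkward fit with 7.5.5.

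The cost is small. AEs are already recorded on the AE CRF (Protocol 13.1.2) and MedDRA-coded (SAP 8.2), and discontinuation reasons are on the eCRF. The work is agreeing the terms, for which the documents give no list, and adding table rows. Sample size and data collection do not change.
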